11.1.2.2 Evaluation of Best Overall Response

The best overall response is the best response recorded from the start of the treatment until disease progression/recurrence (taking as reference for progressive disease the smallest measurements recorded since the treatment started). The patient's best response assignment will depend on the achievement of both measurement and confirmation criteria.

11.1.3 Duration of Response

Duration of overall response: The duration of overall response is measured from the time measurement criteria are met for CR or PR (whichever is first recorded) until the first date that recurrent or progressive disease is objectively documented (taking as reference for progressive disease the smallest measurements recorded since the treatment started).

The duration of overall CR is measured from the time measurement criteria are first met for CR until the first date that progressive disease is objectively documented.

Duration of stable disease: Stable disease is measured from the start of the treatment until the criteria for progression are met, taking as reference the smallest measurements recorded since the treatment started, including the baseline measurements.

11.1.4 Progression-Free Survival

PFS is defined as the duration of time from start of treatment to time of progression or death, whichever occurs first.

11.1.5 Response Review

For determination of response rate and response duration, central review of the PET/CT scans obtained at baseline, after every 2 cycles of therapy, and at final response evaluation is required.

These scans should be burned onto CD and sent via FedEx to the head study coordinator (refer to study contact list at the beginning of the protocol) at DFCI.

The CDs should be labeled with the following information:

1. Patient initials
2. Study number
3. Patient date of birth
- 4. Type of scan – please make sure you specify this**
5. Date of scan
6. Timepoint (baseline, post cycle 2 etc.)

The CDs should be sent to the following address:

[Insert DFCI Study Coordinator's name] #16-712
Dana-Farber Cancer Institute
[name]
[name]

The scan will then be reviewed at the Tumor Imaging Metrics Core at DFCI. We will accept the decision of the treating investigator and local radiology review of scans, however, to determine if a patient remains on study in real time at the time of response assessment.

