5.3 Duration of Therapy

In the absence of treatment delays due to adverse event(s), treatment may continue until one of the following criteria applies or until May 31, 2020. All patients must be off this study treatment by May 31, 2020, as the study treatment will no longer be available.

- Disease progression,
- Intercurrent illness that prevents further administration of treatment,
- Unacceptable adverse event(s),
- Patient decides to withdraw from the study, or
- General or specific changes in the patient's condition render the patient unacceptable for further treatment in the judgment of the investigator.

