5.4 Duration of Follow Up

Patients who discontinue treatment for reasons other than disease progression will be followed with CT scans at 6 and 12 months or until disease progression or next therapy for PFS and DOR endpoints. Follow-up after treatment discontinuation for progression, or after documented progression following discontinuation of therapy for reasons other than progression initially, will be by phone every 6 months for up to 1 year after the discontinuation of treatment for OS endpoints. Patients removed from study for unacceptable adverse event(s) will be followed until resolution or stabilization of the adverse event.

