d: Cycle 2 and on, electrocardiograms (EKGs) will be done on day 1 of each cycle. EKGs should be done per standard of care at the treating institution. EKGs are not required to be in triplicate, but if there is an issue with a QTc value on the single EKG, an average QTc is acceptable on three triplicate EKGs if it makes a patient eligible for treatment.
e: Adverse event and concomitant medication evaluation will be assessed at each visit by the clinical trial personnel.
f: If bone marrow biopsy is negative at screening, it does not need to be repeated. If the bone marrow biopsy is involved at baseline, it must be repeated in order to confirm a complete response (CR).
g: To be collected in 1 x 4 mL purple top EDTA tube. However, a minimum of 1 mL of blood is needed so any tube size that meets this 1 mL minimum is acceptable. This can be shipped along with the frozen tissue.
h: Serum pregnancy test (women of childbearing potential).
i: Off-treatment evaluation. Patients who come off treatment for progression will have telephone follow-up every 6 months for up to 1 year

- | |
|--|
| 
for OS endpoints. Patients who come off treatment for reasons other than progression will have CT scans (see below) at 6 and 12 months, or until the time of progression or next therapy, for PFS and DOR endpoints.
 
j: CT scans will be repeated at 6 and 12 months, or until the time of progression, for patients who come off study for reasons other than disease progression.
 
k: Biopsy or sample of most accessible tissue, which may be bone marrow, body fluid, lymph node, or other tumor site. The sample should be from the same tumor source (ie body fluid, bone marrow, lymph node, or other tumor site) at each timepoint. This is distinct from the bone marrow biopsy required at screening for lymphoma staging. However, if the bone marrow is involved at screening, this can be used as the site of tumor biopsy for patients during pre-treatment, cycle 1 and at the time of progression. Biopsies during cycle 1 should optimally be done on day 17, but can be done between days 17-22.
 |
|--|

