13.4 Analysis of Secondary Endpoints

Secondary endpoints will be analyzed at the same time as the primary endpoint and assessed for each cohort separately and overall. Due to the small sample size in each cohort and all patients combined, secondary endpoints will be descriptive unless otherwise noted. All eligible patients who receive at least one dose of treatment will be included in efficacy endpoints, and all patients regardless of eligibility who receive at least one dose of treatment will be included in toxicity assessments.

Patients receiving any treatment regardless of eligibility or study completion will be assessed for toxicity from the time of their first treatment. At each toxicity evaluation, patients with unacceptable toxicities will be removed from study but remain in safety evaluations. Toxicities will be summarized with counts and proportions within each cohort and overall.

Time-to-event endpoints of progression-free and overall survival (PFS and OS, resp.) will be characterized using the Kaplan-Meier method. OS is defined from the date of study entry until the date of death by any cause. PFS will be measured from the date of study entry until documentation of first progression or death from any cause. Median follow-up time will be assessed using the reverse Kaplan-Meier method.

Duration of response (DOR) is defined as the time from first objective response (PR or CR) until the first date of documented progression using [the response criteria] or death due to any cause. For patient who remain alive without progression, the DOR will be censored on the date of their last response assessment. Patients who begin a subsequent therapy without prior documented progression will be censored at the last response assessment prior to initiation of non-protocol therapy. DOR will be evaluated only in patients who respond with either a PR or CR while on study.

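### Response duration is read centrally, but the local read ends treatment and scheduled scans, so a local progression not called centrally is likely to be censored informatively; PFS has no named reader

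*Combined protocol and SAP*

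**What the plan says.** Section 11.1.5 assigns the endpoint to the central reader: "For determination of response rate and response duration, central review of the PET/CT scans obtained at baseline, after every 2 cycles of therapy". The last evaluation also goes to central review. The same section leaves the real-time decision to the site: "We will accept the decision of the treating investigator and local radiology review of scans, however, to determine if a patient remains on study".

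Under Section 5.3, "treatment may continue until one of the following criteria applies or until May 31, 2020", and disease progression is the first criterion listed. Section 5.4 then separates patients by their reason for stopping. "Patients who discontinue treatment for reasons other than disease progression will be followed with CT scans at 6 and 12 months", or until progression or next therapy. For those who stopped for progression, follow-up "will be by phone every 6 months for up to 1 year after the discontinuation of treatment for OS endpoints". Footnote i of the Section 10 calendar repeats this split. The calendar also marks an FDG-PET/CT in the off-treatment column.

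Section 13.4 ends DOR at documented progression or death from any cause. Otherwise, "For patient who remain alive without progression, the DOR will be censored on the date of their last response assessment"; a responder who starts another therapy without documented progression is censored at the last assessment before it. Section 13.4 does not say whose reading documents progression. The PFS definitions in 11.1.4 and 13.4 name no reader either.

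**The concern.** Two readers are at work, and the one who does not determine DOR decides when scheduled scanning stops. Suppose the site calls progression in a responder and the central reader, looking at the same scan, does not. The patient has already left treatment and the scan schedule, so central review has little or nothing further to read. The patient is then censored because someone judged the disease to be progressing. Kaplan-Meier estimation assumes that censoring carries no information about what follows, and here it probably does.

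At stake is the credibility of the DOR reported for each cohort, which rests on very few responders. A second problem is that the plan is silent on the reader for PFS, so one scan could be a PFS event and a DOR censoring in the same patient.

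**Working it through.** **Plan's own figures.** The documents give no DOR figure. The Simon design figures for MCL and DLBCL reproduce. Early stopping is (1−p)^10: 0.95^10 = 59.9% and 0.75^10 = 5.6% (stated 60% and 5.6%). The exact probability of at least 1 response in 10 and at least 3 in 20 is 6.86% at p = 5% and 88.2% at p = 25% (stated 6.9% and 88%). DOR does not enter these.

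**Tracing the rules** for a responder with local progression that central review does not call:

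| Later course | DOR as written | DOR with local dating |
|---|---|---|
| Alive, no further scan | Censored at about the local-progression scan | Event at that scan |
| Alive, off-treatment PET/CT done later, no central progression | Censored at that PET/CT | Event at the earlier scan |
| Starts new therapy | Censored at last assessment before it | Event at the local-progression scan |
| Dies without new therapy | Event at death | Event at the earlier scan |

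In each row an event becomes a censoring at about the same date or later, or a later event. The recorded duration for that responder is therefore never shorter than with local dating. Turning the event into a censoring can only leave the Kaplan-Meier curve equal or higher. Moving the event to death does the same up to the date of death; after that the curve could dip lower if other responders were censored in between, because the death then falls in a smaller risk set. Section 11.1.3 adds an inconsistency: its DOR definition does not mention death, so under that wording the last row has no event at all.

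**Number of responders.** Three is the minimum for a positive result; a 25% rate gives 0.25 × 20 = 5. One discordant read is then 1/5 = 20% to 1/3 = 33% of responders.

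**Worked example** (illustrative local dates 2, 4, 6, 8, 10 months, all events; median is the first time S ≤ 0.5):

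- All events: S(2) = 4/5 = 0.80; S(4) = 0.80 × 3/4 = 0.60; S(6) = 0.60 × 2/3 = 0.40. Median 6.
- 4-month call censored: S(2) = 0.80; S(6) = 0.80 × 2/3 = 0.53; S(8) = 0.53 × 1/2 = 0.27. Median 8.
- 4-month call runs to death at 12: events at 2, 6, 8, 10, 12. Median 8.
- 6-month call censored: S(4) = 0.60; S(8) = 0.60 × 1/2 = 0.30. Median 8.
- 8- or 10-month call censored: S(6) = 0.40 as before. Median stays 6.
- 2-month call censored: S(4) = 3/4 = 0.75; S(6) = 0.75 × 2/3 = 0.50, exactly on the boundary at 6.

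**Direction against the central yardstick.** A simulation of 200,000 responders per scenario compared the written rule with scanning continued to central progression and with local dating. None of its assumptions comes from the documents except the 8-week scans and the 1-year telephone follow-up: exponential time to progression with median 6 months, median 8 months from central progression to death, and 0, 50 or 100% starting new therapy at the local call. The off-treatment PET/CT was not modelled. Mean DOR restricted to 24 months, when the local call comes one or two scans before central progression:

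| Responders discordant | Written rule | Continued central scanning | Local dating |
|---|---|---|---|
| 8% | 9.3–9.5 | 9.0 | 8.8 |
| 16% | 9.7–9.9 | 9.0 | 8.6 |
| 24% | 10.1–10.5 | 9.0 | 8.4 |
| about 40% | 10.9–12.0 | 9.0 | 8.0 |

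At 24% the medians are 8.1–9.2, 7.4 and 5.5 months. If instead the local call is pure noise, the written rule gives 8.9–9.0 months against 9.0 with continued scanning, so there is no upward bias on that yardstick. Local dating is then too short, at 7.1–8.7.

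**The case against.** The plan's chosen yardstick is central review. Against it, upward bias is not a certainty: it disappears if the local call is noise and stopping treatment changes nothing. This stands, and the direction has to be stated conditionally.

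A reader might infer that DOR is inflated by a fixed factor 1/(1−d) when a fraction d of local progressions is not called centrally, giving 1/0.8 = +25% or 1/0.7 = +43%. The documents do not support this. They give no discordance rate, and the formula ignores deaths, which 13.4 counts as events. At d = 24% it gives 1/0.76 = +32%, whereas the simulated median is 8.1/7.4 = +9% to 9.2/7.4 = +24% above continued scanning. The two fractions are defined on slightly different bases, so the comparison is approximate.

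A reader might also infer that progression can never be documented after the local call. The calendar marks one off-treatment PET/CT, and 11.1.5 sends the final evaluation to central review, so one further central read may exist. It is not continued surveillance.

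Section 13.4 names no reader for documented progression. If a local reading sufficed, the censoring problem would go, but 11.1.5 would be contradicted. Nor does any text assign PFS and DOR to different readers; the possible mismatch comes from silence.

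Finally, DOR is secondary and descriptive, in responders only, and individual durations can be listed. That limits the consequence but does not settle which date goes in the list.

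**Conclusion.** The gap is real. Followed as written, the plan can censor a responder for DOR because the site judged the disease to be progressing, and no other section resolves a local/central disagreement. The direction is firm only against local dating, where each affected responder's recorded duration is equal or longer. Against central progression the bias is upward when the local call foreshadows it; a rise in risk after stopping treatment should act the same way, but that is reasoned, not simulated. The size cannot be stated from the documents. One discordant read among 3 to 5 responders may move the median, as from 6 to 8 months in the example, or may not move it at all.

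The conclusion rests on two readings: that 11.1.5 governs the progression date for DOR, and that Kaplan-Meier applies to DOR, which 13.4 names only for PFS and OS but implies by its censoring rules. A reader might go on to doubt the go/no-go decision; this DOR issue gives no ground for that, because the response rules do not use DOR. This is a cheap improvement.

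**What to change.** In Section 13.4:

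- Name the same progression source for PFS and DOR, keeping central review for DOR as 11.1.5 requires.
- Pre-specify a parallel DOR and PFS analysis in which the investigator-determined progression that ended treatment also counts as an event on its date, whether or not central review calls it.
- Report the number of discordant local/central reads, and list each responder's duration under both readings.

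Settle this before the two sets of reads are compared, so that the event rule cannot depend on them. It needs no new scans and changes no patient management.

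The cost is the wording and one extra table. The local-event DOR will be shorter and may date progression early: at 24% discordance the simulated median is 5.5 months against 7.4 with continued scanning. For that reason it should stand beside the central analysis and not replace it; the two together roughly bracket the answer.

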12. STUDY OVERSIGHT AND DATA REPORTING / REGULATORY REQUIREMENTS

Adverse event lists, guidelines, and instructions for AE reporting can be found in Section 7.0 (Adverse Events: List and Reporting Requirements).

12.1 Study Oversight

This protocol is monitored at several levels, as described in this section. The Protocol Principal Investigator is responsible for monitoring the conduct and progress of the clinical trial, including the ongoing review of accrual, patient-specific clinical and laboratory data, and routine and serious adverse events; reporting of expedited adverse events; and accumulation of reported adverse events from other trials testing the same drug. The Protocol Principal Investigator and statistician have access to the data at all times through the CTMS web-based reporting portal.

For this Phase 2 portion of the study, the Protocol Principal Investigator will have, at a minimum, quarterly conference calls with the Study Investigators and the CTEP Medical Officers to review accrual, progress, and pharmacovigilance. Decisions to proceed to the second

stage of a Phase 2 trial will require sign-off by the Protocol Principal Investigator and the Protocol Statistician through IWRS and Medidata Rave.

All Study Investigators at participating sites who register/enroll patients on a given protocol are responsible for timely submission of data via Medidata Rave and timely reporting of adverse events for that particular study. This includes timely review of data collected on the electronic CRFs submitted via Medidata Rave.

All studies are also reviewed in accordance with the enrolling institution's data safety monitoring plan.

12.2 Data Reporting

Data collection for this study will be done exclusively through Medidata Rave. Access to the trial in Rave is granted through the iMedidata application to all persons with the appropriate roles assigned in the Regulatory Support System (RSS). To access Rave via iMedidata, the site user must have an active CTEP IAM account (check at < <https://ctepcore.nci.nih.gov/iam> >) and the appropriate Rave role (Rave CRA, Read-Only, RAVE CRA, SLA or Site Investigator) on either the LPO or participating organization roster at the enrolling site. To hold the Rave CRA role or RAVE CRA (Lab Admin) role, the user must hold a minimum of an AP registration type. To hold the Rave Site Investigator role, the individual must be registered as an NPIVR or IVR. Associates can hold read-only roles in Rave.

Upon initial site registration approval for the study in RSS, all persons with Rave roles assigned on the appropriate roster will be sent a study invitation e-mail from iMedidata. To accept the invitation, site users must log into the Select Login (<https://login.imedidata.com/selectlogin>) using their CTEP-IAM user name and password, and click on the "accept" link in the upper right-corner of the iMedidata page. Please note, site users will not be able to access the study in Rave until all required Medidata and study specific trainings are completed. Trainings will be in the form of electronic learnings (eLearnings), and can be accessed by clicking on the link in the upper right pane of the iMedidata screen.

Users that have not previously activated their iMedidata/Rave account at the time of initial site registration approval for the study in RSS will also receive a separate invitation from iMedidata to activate their account. Account activation instructions are located on the CTSU website, Rave tab under the Rave resource materials (Medidata Account Activation and Study Invitation Acceptance). Additional information on iMedidata/Rave is available on the CTSU members' website under the Rave tab or by contacting the CTSU Help Desk at [name] or by e-mail at [contact].

12.2.1 Method

This study will be monitored by the Clinical Trials Monitoring Service (CTMS). Data will be submitted to CTMS at least once every two weeks via Medidata Rave (or other modality if approved by CTEP). Information on CTMS reporting is available at: <http://www.theradex.com/clinicalTechnologies/?National-Cancer-Institute-NCI-11>. On-site

audits will be conducted on an 18-36 month basis as part of routine cancer center site visits. More frequent audits may be conducted if warranted by accrual or due to concerns regarding data quality or timely submission. For CTMS monitored studies, after users have activated their accounts, please contact the Theradex Help Desk at [contact] or by email at [contact] for additional support with Rave and completion of CRFs.

12.2.2 Responsibility for Data Submission

For ETCTN trials, it is the responsibility of the PI(s) at the site to ensure that all investigators at the ETCTN Sites understand the procedures for data submission for each ETCTN protocol and that protocol specified data are submitted accurately and in a timely manner to the CTMS via the electronic data capture system, Medidata Rave.

Data are to be submitted via Medidata Rave to CTMS on a real-time basis, but no less than once every 2 weeks. The timeliness of data submissions and timeliness in resolving data queries will be tracked by CTMS. Metrics for timeliness will be followed and assessed on a quarterly basis. For the purpose of Institutional Performance Monitoring, data will be considered delinquent if it is greater than 4 weeks past due.

Data from Medidata Rave and CTEP-AERS is reviewed by the CTMS on an ongoing basis as data is received. Queries will be issued by CTMS directly within Rave. The queries will appear on the Task Summary Tab within Rave for the CRA at the ETCTN to resolve. Monthly web-based reports are posted for review by the Drug Monitors in the IDB, CTEP. Onsite audits will be conducted by the CTMS to ensure compliance with regulatory requirements, GCP, and NCI policies and procedures with the overarching goal of ensuring the integrity of data generated from NCI-sponsored clinical trials, as described in the ETCTN Program Guidelines, which may be found on the CTEP (http://ctep.cancer.gov/protocolDevelopment/electronic_applications/adverse_events.htm) and CTSU websites.

An End of Study CRF is to be completed by the PI, and is to include a summary of study endpoints not otherwise captured in the database, such as (for phase 1 trials) the recommended phase 2 dose (RP2D), and a description of any dose-limiting toxicities (DLTs). CTMS will utilize a core set of eCRFs that are Cancer Data Standards Registry and Repository (caDSR) compliant (<http://cbiit.nci.nih.gov/ncip/biomedical-informatics-resources/interoperability-and-semantics/metadata-and-models>). Customized eCRFs will be included when appropriate to meet unique study requirements. The PI is encouraged to review the eCRFs, working closely with CTMS to ensure prospectively that all required items are appropriately captured in the eCRFs prior to study activation. CTMS will prepare the eCRFs with built-in edit checks to the extent possible to promote data integrity.

Further information on data submission procedures can be found in the ETCTN Program Guidelines (http://ctep.cancer.gov/protocolDevelopment/electronic_applications/adverse_events.htm).

